3.0 Intervention to be studied

Participants in all groups will have already undertaken their voice care (voice assessments and voice therapy with a certified SLP) at MUSC. Depending on their group assignment, participants will also receive either inspiratory training, expiratory training, or no respiratory intervention (standard of care group). The experimental and standard of care interventions are described below.

Inspiratory Training [Experimental intervention]: Inspiratory training will be conducted using an inspiratory pressure threshold trainer (Philips Respironics® Threshold IMT or POWERbreathe® Medic Plus, for patients with a MIP of 55 cmH₂0 and over), which consists of a mouthpiece with a spring-loaded valve(13, 25). The valve blocks the airflow until the threshold pressure is achieved and allows airflow as long as the sufficient pressure is maintained. The threshold will be set at 75% of the participant's initial MIP, as reported in the literature with elderly participants(16). If it is too hard for the participant, the load will be lowered until the participant is able to perform the exercises. The load will be adjusted weekly by the study team member to maintain a threshold at 75% of the participant's MIP. Daily practices will consist of 5 sets of 5 breaths with the device with a break between sets, repeated twice daily (15, 18, 31).

Expiratory Training [Experimental intervention]: Expiratory training will be conducted using an expiratory pressure threshold trainer (EMST150TM) which consists of a mouthpiece with a spring-loaded valve. The valve blocks the airflow until the threshold pressure is produced (set at 75% of the participant's initial MEP, per literature with similar age groups(32-34)), and allows the airflow as long as the sufficient pressure is maintained. Participants will be asked to exhale forcefully into the mouthpiece after a full inspiration. If it is too hard for the participant, the load will be lowered until the participant is able to perform the exercises. The load will be adjusted weekly by the study team member to maintain a threshold at 75% of the participant's MEP. Daily practices will consist of 5 sets of 5 breaths with the device with a break between sets, repeated twice daily(32-34).

Inspiratory and expiratory training have never been conducted on patients with presbyphonia. To determine the adequate intensity and duration of treatment, we reviewed the literature of respiratory training interventions with patients of similar age groups. We decided on a threshold of 75% of MIP and MEP because 1) this value was widely used across studies, resulted in significant improvements in respiratory outcomes, and has been shown to be safe(16, 32-34); 2) maximal improvements in muscle strength have been reported to occur with a loading at 70-90% of the maximal strength(14). The regimen of 5 sets of 5 breaths was also widely used across studies, along with a threshold at 75% of MIP/MEP, and resulted in improved respiratory outcomes. We chose to have the participants practice their exercises every

day of the week because in our opinion it is the best way to create a habit and therefore enhance compliance to treatment.

Voice Exercises [Standard of care intervention]: Participants will be instructed to follow the four steps of the VFE protocol, developed by Stemple (35) and commonly used by SLPs with patients with presbyphonia: (a) sustain the vowel /i/ on the musical note F (above middle C for women; below middle C for men) for as long as possible. (b) Glide from the lowest note to the highest note on the word "knoll". (c) Glide from the highest note to the lowest note of the word "knoll". (d) Sustain the notes C-D-E-F-G (starting from middle C for women and an octave below middle C for men) on the word "oll", for as long as possible. Each note will be repeated until the participant finds the right placement (forward-focused voice), as judged by the SLP. Humming exercises will be used to facilitate placement. Daily practices, 2x/day, will consist of two repetitions of the VFE protocol for the IMST and EMST groups and four repetitions of the VFE protocol for the VFE group. Recordings of the therapy sessions will be provided to facilitate home practice.

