There are two main types of respiratory training: inspiratory training, also called inspiratory muscle strength training (IMST), and expiratory training, also called expiratory muscle strength training (EMST). In this application, we propose a novel, proof-of-concept study to test whether the addition of either type of respiratory training to the standard of care voice therapy (voice exercises) enhances respiratory and voice outcomes. This study will permit, for the first time, the comparison between inspiratory and expiratory training. The theoretical framework is: inspiratory training strengthens the inspiratory muscles and thus increases both vital capacity and the ability to counteract passive recoil of the lungs, improving

the quantity of and control over the airflow available to drive the vocal folds. Expiratory training strengthens the expiratory muscles to expand the expiratory reserve volume and provide more airflow for voicing. Using pulmonary function tests and respiratory pressure measures, combined with voice assessments, we will specifically evaluate our hypotheses and determine the independent effects of inspiratory training and expiratory training on respiratory function and voice production. We will also evaluate the interaction between the type of respiratory training and a patient's baseline respiratory function. This will provide mechanistic information to guide the future selection of the type of respiratory training to augment voice therapy, to promote an impairment-specific intervention paradigm.

Forty-eight participants diagnosed with presbyphonia will be included in the study and will be stratified and blocked-randomized into one of the three intervention groups (two experimental groups and one control group), using a 3-parallel arm design: 1) inspiratory training (IMST) (experimental group), 2) expiratory training (EMST) (experimental group), or 3) voice exercises (VFE) (control group), delivered four times during a 60-minute therapy session. Monitored home practice will consist of 10 minutes of twice daily exercise for the duration of therapy. Participants from all three groups will carry on with their standard of care voice therapy with a certified SLP.

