Specific Aim 1: To measure the effects of respiratory training on respiratory and voice outcomes in patients with presbyphonia. Hypothesis 1: The respiratory training groups (inspiratory and/or expiratory) will demonstrate greater improvement in respiratory outcomes, measured through pulmonary function tests and respiratory pressure measures, compared with the voice exercises-only group. Hypothesis 2: The respiratory training groups (inspiratory and/or expiratory) will demonstrate greater improvement in voice-related outcomes than the voice exercises-only group.

Secondary Aim 1: To assess the reliability of the ratings for subjective outcomes (videostroboscopy ratings and perceptual judgements of voice quality). Hypothesis 1: Intra-judge reliability will be of at least 80%. Hypothesis 2: Inter-judge reliability will be of at least 70%.

Specific Aim 2: To determine how baseline measures of respiratory function influence the effects of respiratory training (respiratory and voice outcomes). Hypothesis 1: inspiratory training will have maximal effect on patients with decreased maximum inspiratory pressure (MIP). Hypothesis 2: Expiratory will have maximal effect on patients with decreased maximum expiratory pressure (MEP).

This is an initial feasibility and mechanistic study that has the potential to reveal that respiratory training can significantly improve outcomes from voice therapy by acting in synergy with voice exercises. Currently,

much time is spent in voice therapy on subthreshold 'breathing exercises' that lack evidence. This project will provide guidance for evidence-based and theory driven approaches to leverage respiratory function to improve voice therapy. Conversely, negative findings from this study would indicate that respiratory function is ineffective and not a viable target for therapy in this patient population.

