10.0 Study Design / Methods

Overview

After being enrolled in the study, treatment-seeking patients with a diagnosis of presbyphonia will undergo baseline respiratory assessments including spirometry and respiratory muscle strength measures as well as voice recordings (acoustic assessments). Participants will then be blocked-randomized (based on their MIP and MEP) to one of three groups using a 3-parallel arm design: (2 experimental groups and 1 control group), using a 3-parallel arm design: 1) inspiratory training (IMST) (experimental group), 2) expiratory training (EMST) (experimental group), or 3) standard of care (VFE) (control group), delivered four times (see table 1 for participant timeline). The sessions will occur on the same days as the participants' scheduled voice therapy sessions when possible. Participants will be asked to practice their respective exercises for 10 minutes, twice daily, seven days a week during the duration of the study. A final assessment session, after the 4th therapy session, will mirror the baseline measures. Participants will receive a monetary compensation of \$20 for each study visit, for a maximum of \$80 for the whole study. Payments will be made via cash. Outcomes that rely on subjective judgment (visual ratings of

videostroboscopy and perceptual judgments of voice quality) will be rated by trained judges (SLPs) blinded to the group assignment. [**Note**: Long-term follow-up will not be conducted. This study's focus is on the mechanistic effects of the intervention; future studies, given positive outcomes from this study, will explore the effectiveness and long-term effects.]

Table 1: Participant Timeline

Visit 1	Visit 2	Visit 3	Visit 4
Baseline assessment session			
Therapy session 1	Therapy session 2	Therapy session 3	Therapy session 4
			Final assessment session

Patient Participants

Standard of Care Assessments (Procedures being performed already for diagnostic purposes)

- Laryngeal imaging: prior to the examination, the laryngologist will administer topical lidocaine and neosynepherine in a spray to one of the nasal cavities. The laryngologist then passes the camera through the nose to examine the vocal folds. The participant will be asked to sustain phonation on the vowel /i/ for at least 3 seconds and to repeat with pitch and loudness variations.

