- Acoustic Assessments: The microphone is positioned at a 45° angle and at a standardized distance from the mouth of the participant. The participant is asked to sustain phonation on the vowel /a/ at a comfortable loudness for 3-5 seconds and as loud as possible for 2 seconds, and to glide to a high pitch and to a low pitch. They are then asked to read the 6 CAPE-V sentences and to have a

short natural conversation with the speech therapist. The participant is then asked to rate their perceived phonatory effort (PPE) on a scale.

- Self-assessments: The participant is asked to fill out the Voice Handicap Index questionnaire, the Reflux Symptom Index, and the Glottal Function Index.
- Aerodynamic assessments: The participant wears a face mask over the nose and mouth, which directs the air flow. A tube connected to a pressure transducer is passed through a hole in the mask, and inserted between the lips. The participant is asked to produce short utterances each comprised of minimally five /pi/ syllables at a rate approximating 1.5 2 syllables per second (/pi-pi-pi-pi-pi/). Each string of at least five syllables should be produced on one breath/exhalation. The task is repeated 3 times at comfortable pitch and loudness.

Standard of Care Intervention (Procedures being performed already for treatment purposes)

- Vocal Function Exercises: Participants in all 3 groups will be instructed to follow the 4 steps of the Vocal Function Exercises (VFE) protocol, developed by Stemple (2005) and commonly used by speech language pathologists (SLP) with voice patients: (a) sustain the vowel /i/ on the musical note F (above middle C for women; below middle C for men) for as long as possible. Repeat as judged by the SLP. (b) Glide from the lowest note to the highest note on the word "knoll". Repeat as judged by the SLP. (c) Glide from the highest note to the lowest note of the word "knoll". Repeat as judged by the SLP. (d) Sustain the notes C-D-E-F-G (starting from middle C for women and an octave below middle C for men) on the word "oll", for as long as possible. Each note will be repeated until the participant finds the right placement (forward-focused voice), as judged by the SLP. Humming exercises will be used to facilitate placement of the voice.
- Counseling and patient education during the therapy sessions.

Experimental Assessments (Procedures to be performed solely as part of this research study):

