Expiratory training: During the expiratory training exercises, the patient has to generate sufficient expiratory effort to open a threshold valve and allow air to flow. The action increases the intraoral and intrathoracic pressures and has been compared to a sub-maximal Valsalva maneuver (54), which has been associated with blood pressure, heart rate changes and abnormal cardiac findings (55). However, expiratory training is not comparable to a typical Valsalva maneuver for two reasons: 1) the duration of the isometric muscle contraction during expiratory training is of approximately 2 seconds, which is much shorter than during a typical Valsalva maneuver (15-20 seconds) (54, 56); 2) during expiratory training, complete closure of the glottis rarely occurs, and when it does it is very briefly (54). Laciuga et al. (54) tested the effect of expiratory training on young health adults and found no acute changes in cardiovascular response (heart rate, blood pressure, oxygen saturation) and no adverse events following a session of 25 expiratory training trials. However, expiratory training is not recommended in older patients with certain cardiovascular disease or with untreated hypertension (18). Thus, patients with any diseases that are judged by the physician to put the patient at risk will be excluded from participating in this study.

Expiratory training is currently used in clinics and in research with various patient populations of the same age group as patients with presbyphonia, including patients with Parkinson's disease, multiple sclerosis and subacute stroke, as well as sedentary elderly participants (18, 30, 53, 57). No serious adverse events have been reported in the literature. Nonetheless, it is suggested that patients be cleared by a physician before undergoing expiratory training. We will follow this recommendation.

Incidental findings: Spirometry and muscle pressure evaluations are screening tests and therefore no diagnosis will be made based on the patients' performance.

Risks associated with randomization: This study's goal is to test the effectiveness of two types of intervention (inspiratory training and expiratory training) and to compare them to usual care received by voice patients when working with SLPs (voice exercises only). There is a chance that undergoing respiratory training may be less effective than using the additional time to work on voice exercises.

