16.0 Potential Benefits to Subjects or Others

The experimental groups may benefit from receiving a respiratory training intervention. Respiratory training directly targets the respiratory system and *could* lead to greater improvements in both respiratory and voice outcomes than those observed with voice therapy alone.

There is a possibility that the participant will not directly benefit from being part of this research project.

For the subjects of the study, as well as for future voice patients who could benefit from this intervention if it were to be proven effective and to be implemented in common usual care, it could lead to important benefits:

- Improved respiratory and voice outcomes;
- Greater improvements in a person's daily activities involving communication;
- Reduced number of voice therapy sessions needed
- Improved voice-related quality of life

Because communication is a social activity, these benefits are also susceptible to impact the quality of life of the participants' significant other, family and caregiver.

The minimal risks associated with this research project are reasonable in relation to the potential benefits to the study participants and others. In the case where the intervention is not shown to be more efficacious than voice therapy only, the subjects would still receive the benefits from standard of care voice therapy.

Participant-raters will be compensated at a rate of \$40 for every 10-rating package (one package includes an endoscopy recording and an audio file). It is estimated that each rater will rate a total of 39 packages, for a total of \$160 for their participation in the study.

Both patient participants and participant raters may indirectly benefit, along with other patients, clinicians and society from the dissemination and implementation of the results of this research. The results of this research if in-line with our pilot data, will provide evidence that will serve as a guide for speech-language pathologists to inform patient management decisions. In general, any study that improves the effectiveness of voice intervention and the evidence upon which treatment recommendations are based may improve the health status and quality of life of patients and decrease the economic burden of voice disorders. These benefits outweigh the minimal risks that may result from loss of confidentiality and discomforts associated with the respiratory training interventions.

Importance of the Knowledge to be Gained

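### The training arms do half the control arm's home VFE in the same practice time, so a null voice result cannot support the negative conclusion that Section 1.0 draws in advance

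*Combined protocol and SAP*

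**What the plan says.** **The question.** Section 1.0 says the study tests whether "the addition of either type of respiratory training to the standard of care voice therapy" improves respiratory and voice outcomes. Section 3.0 keeps the same framing: depending on assignment, "participants will also receive either inspiratory training, expiratory training, or no respiratory intervention (standard of care group").

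**The home regimen.** Under Voice Exercises, Section 3.0 sets twice-daily practice at "two repetitions of the VFE protocol for the IMST and EMST groups and four repetitions of the VFE protocol for the VFE group". The training arms also do five sets of five loaded breaths at each practice. Practice time does not differ by arm: Section 10.0 asks participants to "practice their respective exercises for 10 minutes, twice daily, seven days a week", and Section 1.0 gives the same 10 minutes twice daily. All three groups continue voice therapy with a certified speech-language pathologist (SLP).

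**The reading of a negative result.** Section 1.0 states that "negative findings from this study would indicate that respiratory function is ineffective and not a viable target for therapy in this patient population". Section 16.0 is more cautious. It covers the case in comparative terms ("In the case where the intervention is not shown to be more efficacious than voice therapy only"), and under Importance of the Knowledge to be Gained it says only that negative findings would raise questions about relevance. Section 15.0 mentions the trade-off as a risk of randomization: "There is a chance that undergoing respiratory training may be less effective than using the additional time to work on voice exercises".

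**The concern.** The question is framed as an addition, but at home the regimen is a substitution: the loaded breaths take the place of two of the four VFE repetitions. If extra VFE helps the voice, control has an advantage on voice outcomes that is unrelated to respiratory training.

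This matters most for a plausible mixed result, in which respiratory pressures improve in the training arms but voice outcomes do not differ from control. Read as Section 1.0 is written, that result could be used to dismiss a treatment that helps when added to a fixed amount of VFE. The data could not support such a dismissal.

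**Working it through.** The plan computes no figure on this point. The check is a dose count followed by what each contrast can estimate.

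**Inputs**
- VFE repetitions per home practice: 2 in IMST and EMST, 4 in control (Section 3.0).
- Practices per day: 2, seven days a week (Sections 3.0 and 10.0).
- Loaded breaths per practice in the training arms: 5 × 5 = 25 (Section 3.0).
- Practice time: 10 minutes per practice in every arm (Sections 1.0 and 10.0).

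**Home dose**

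| | IMST or EMST | Control |
|---|---|---|
| VFE repetitions per day | 2 × 2 = 4 | 4 × 2 = 8 |
| VFE repetitions per week | 4 × 7 = 28 | 8 × 7 = 56 |
| Loaded breaths per day | 25 × 2 = 50 | 0 |
| Practice time per day | 10 × 2 = 20 min | 10 × 2 = 20 min |

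The home VFE ratio is 28/56 = 0.5.

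**Total dose.** Let S be the weekly number of VFE repetitions done in therapy sessions. Assume it is equal across arms; the documents give no count. The ratio of total VFE is then (28 + S)/(56 + S), which exceeds 0.5 whenever S is above zero. So the halving applies to home practice, and the overall difference may be smaller.

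**What the voice contrast estimates.** For any voice outcome scored so that higher is better, let R be the effect of respiratory training given on top of two home repetitions. Let V be the effect of going from two to four home repetitions.
- Training arm minus control = R − V.
- IMST minus EMST = R(IMST) − R(EMST). V cancels because both arms do two repetitions.

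**What a null means.** A true difference of zero says R = V. That fits R = V = 0 (training does nothing) and equally R = V > 0 (training helps, and so does the VFE given up). Separating the two needs either an arm with two repetitions alone or an outside value for V. The design has no such arm and the documents give no VFE dose-response.

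**Whether the analysis can recover R.** The Aim 1 model in Section 12.0 has time (two levels) and intervention (three levels). A term for prescribed VFE dose would not help, because dose is fixed by arm: every trained participant is assigned two repetitions and every control four. The compliance journal records practice, but differences in adherence are not randomized.

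**What a positive result means.** R − V > 0 implies R > V. If extra VFE does no harm (V ≥ 0), then R > 0. A positive voice result stays valid and is conservative.

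**Other comparisons.** MIP, MEP and spirometry are less exposed to VFE dose, so Hypothesis 1 is less affected. Aim 2 looks at who improves after inspiratory or expiratory training, and both arms carry the same home VFE, so it is unaffected.

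**The case against.** **Time-matching is a legitimate design.** It stops extra practice time from explaining a benefit. It also fits the practical question in Sections 2.0 and 16.0 of how best to use limited therapy time. If training does not beat the same time spent on VFE, that bears on its usefulness. This stands, and the regimens should not change. It supports a comparative conclusion, though, and Section 1.0 states an absolute one.

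**It is one sentence of aims text.** Nothing in Section 12.0 uses it, no go/no-go step depends on it, and the same paragraph calls the study an initial feasibility and mechanistic one. Sections 15.0 and 16.0 are already more careful. This stands, and it is why the point is minor. But those sections leave the Section 1.0 sentence uncorrected, and that sentence sets in advance how a negative result will be read.

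**The usual VFE dose is not stated.** Four repetitions might be extra practice to fill the control arm's time, in which case describing training as an addition would be accurate for the training arms. The standard-of-care label on control points the other way, and the documents do not settle it. The contrast is R − V in either case.

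**Stronger readings that a reader might infer**
- *The comparison is invalid.* It is not. Hypothesis 2 asks whether the training groups improve more than the voice-exercises-only group, and the design answers that for the regimens as given.
- *Trained participants receive half the VFE overall.* The split is stated for home practice only, and all arms continue SLP therapy.
- *A known amount of effect or power is lost.* Without a dose-response, V cannot be sized.
- *Section 10.0 contradicts the dose split.* Its statement that "Participants in all 3 groups will be instructed to follow the 4 steps of the Vocal Function Exercises (VFE) protocol" introduces the exercise steps and sets no home dose, so there is no conflict.

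**Conclusion.** The point holds for voice outcomes and for the reading of a negative result. Home VFE is 4 against 8 repetitions a day within equal practice time, so each training-versus-control voice contrast is R − V and not the pure add-on effect R. A null voice result supports only a comparative statement. It cannot show that respiratory function is ineffective or should be abandoned as a target.

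This rests on the regimens being followed as Section 3.0 prescribes and on V not being known to be negligible. V may in fact be zero, but the Section 1.0 sentence needs it to be negligible and nothing in the documents establishes that. The conclusion does not depend on sample size or power.

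Severity is minor: the trial remains valid, and the defect lies in the add-on framing and one sentence of interpretation.

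**What to change.** Make two wording edits in Section 1.0. Leave the regimens, Hypothesis 2 and Section 16.0 as they are.

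1. Where the study question is introduced, describe the voice comparison with control as time-matched: IMST or EMST plus two VFE repetitions, against four VFE repetitions, per home practice.
2. Replace the sentence on negative findings with:

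> A negative voice result would mean no evidence that respiratory training with reduced home VFE improves voice outcomes more than voice therapy with the same home practice time spent entirely on VFE; it would not show that respiratory training adds nothing to a fixed VFE dose. A negative respiratory result would raise questions about this training regimen in this population.

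The cost is a narrower stated conclusion. Conduct, sample size and analysis do not change.
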